8.2 Statistical analysis of the secondary efficacy endpoint(s)

There are several secondary endpoints that cover each of the secondary objectives and a list is provided in the table listing the secondary endpoints in Section 2.2.1.2. Some of these endpoints are different derivations from the same collected data. In addition, some of the endpoints collected for one objective, may be the inputs to derivations for endpoints for the same objective or for another objective.

Data types for the secondary efficacy endpoints fall into the following main categories: continuous (for example, change from baseline (including the various ordinal categorical endpoints), number of days with 'condition'), ordinal categorical, binary ('responder' Y/N), time to event or duration of event.

Table 8.1 describes the analyses of each secondary endpoint listed in Section 2.2.1.2 and identifies which efficacy objective (2-6) the endpoint is addressing. Brief details of any derivations and analysis methods used are provided. Further details are included in the mock TFL shell document. In the event the data for some of these endpoints indicate that analysis through fitting models is not appropriate, for example too few events for a formal analysis on response or mortality rates, or time to event analyses, the analyses will not be carried out and only listings, figures and summaries provided.

Some patients may withdraw from the study or be transferred to another hospital prior to discharge through medical improvement. If data have been collected from another hospital post discharge from the first hospital, these data will be listed. This will be for variables or derived variables which would have included data from these patients. For example, duration of stay in hospital. However, for variables only including data up to a relative day prior to discharge/transfer from the first hospital, these patients will be included in the analysis/summary

for that period but set as missing for the other periods. Residual plots will be reviewed to determine any influence these participants may have had on the results.

Table 8.1

Endpoint	Derivation	Analysis

Objective 2 Incidents of participants reporting each severity rating in 6-point ordinal scale at D1, D6, D15 and D28
	
Percentages for each ordinal score on each day are based on N in each treatment arm on D1. An additional category (score=7) to be created to indicate participants who have withdrawn from the study for any reason or transferred to another hospital. Add label for score category=7 as ‘Withdrawn’. Participants who die (score=1) or are discharged from hospital due to medical improvement (score=6) or are withdrawn (score=7) remain in both the numerator and denominator for these categories on subsequent days by using LOCF for discharge, death and withdrawal. Only use LOCF for participants whose final recorded score is 1, 6 or 7. For the interim, all other subjects whose final recorded score during the period up to 28 days is not equal to 1, 6 or 7, impute a score of 8 for their remaining days (up to D28). This is to indicate the percentage of participants who are still on treatment without imputing what their future values may be.
 
Check that ordinal score matches whether participant has been discharged or has died
	
PROC FREQ to create summary table of actual counts and percentages for each of the 6-points on the ordinal scale on each nominal day (D1, D6, D15 and D28) for each treatment
 
Stacked 100% bar chart indicating a snapshot of counts in each category (color coded for scores 1-7 (including 8 in the interim analyses)) on each relative day by treatment arm. A separate graph for each treatment, placed side by side.
 
For final analysis:
 
Logistic regression for data from specified nominal days (D1, D6, D15 and D28). Fixed effect of Score*Treatment indicating whether the pattern across scores is different between treatments on each day.
 
Note: If D1 is pre-dose and therefore baseline, exclude from table and plot.

Endpoint	Derivation	Analysis

Objective 2
 
Change from baseline in 6-point ordinal scale to Day 6, Day 15 and Day 28
	
Change from baseline at each relative day for each participant. If a participant has died (score=1) or discharged from hospital (score=6), these values will carry forward onto subsequent days. For participants who are missing values after any day for any other reason, the value will remain missing. For participants who miss some intermediate values, the latest value prior to the missing value will be carried forward until the day where data are recorded again.
 
The additional scores derived for the previous endpoint will not be used in change from baseline
 
(One line per day per participant dataset)
	
Summary table providing n, mean change from baseline, SD change from baseline, median, minimum and maximum on each specified nominal day by treatment arm
 
Graph of change from baseline over time for each participant by treatment, and the average lines for each treatment.
 
For final analysis: MMRM fitting response variable change from baseline against fixed effects for specified nominal days, treatment and treatment*nominal day interaction. Baseline score as covariate and baseline score*nominal day as additional terms. Participant as random effect.

Objective 2
 
Time to at least a 2-point improvement or discharge sustained up to (D15 for interim analysis 1) D28 on the 6-point ordinal scale during 28-day assessment period (=Response)
 
Note: for both the interim analyses and final analyses up to D15 and D28 respectively, if the 2-point change occurred on D15 or D28, and the
	
Create TTE dataset for cumulative response rate analysis with 2 variables each for analysis up to D15 and up to D28 with one line per participant providing time to response and censor status. Censor status=0 for patients with response and =1 on relative day for: patients who have: withdrawn from treatment and/or study; discharged from first hospital for reasons other than improvement; have no response by analysis date (censor=1 at analysis
	
Kaplan-Meier analysis using PROC LIFETEST. Strata ACTARM.
 
Request Failure plot adjusting axis and heading titles to reflect responder and not failure
 
Output statistics:
 
Appropriate statistics from analysis as indicated in mock shell

Endpoint	Derivation	Analysis

patient remained in hospital, the patient will be classified as a responder, even though the 2-point change had not been ‘sustained’.
	
date). If Time to Response >15 and censor=1 for analysis up to D15, Time to Response=15. If Time to Response >28 and censor=1 for analysis up to D28, Time to Response=28. For patients who have died Time to Response is set to D15 or D28 respectively and censored at this time. Note: Treatment will be merged into the TTE dataset. In addition to other variables that may be used as covariates in final analysis.
 
(one line per participant dataset)
	

Objective 2 Percentage of participants reporting at least a 2-point improvement sustained to D28 or discharge
	
Use D28 response indicator variable defined above
	
PROC FREQ/PROC LOGISTIC(if covariates are added) Model: Response=ACTARM +covariates (if added) Output percentage response on each treatment. Odds ratio and 95% confidence interval

Objective 2 AUEC/Time using the 6-point score recorded daily – up to D15, D28 and all data recorded
	
For each participant calculate the area under the curve and divide by 15 for up to D15 and by 28 for up to D28 (higher average score per day the better the response). Use last value brought forward for any missing values until next data entry. For discharge, carry forward score=6 for each day post discharge day. For death, carry forward score=1 for each day post death day.
	
Analyse AUEC/Time using analysis of variance with ACTARM as a two-level factor and baseline score as a covariate

Endpoint	Derivation	Analysis

Objective 2 Percentage of participants who record at least 2-point improvement from baseline or discharge (response) between D1-D6, D7-D15 and D16-D28
	
Responder classified as above. Create indicator variable (3 levels) if the relative day of START of response is between D1 and D6, between D7 and D15 or between D16 and D28. Each responder participant can only be within one of these categories. Participants who have a missing value are classified as non-responders
	
Frequency table and percentage responders in each of the categories defined by the indicator variable, by treatment. Exact 95% confidence intervals for each percentage


Objective 2 Percentage of participants not deteriorating according to the ordinal scale by 1 point between D1 and D6, between D7 and D15 and between D16 and D28 – not deteriorating corresponds to Stable + Responders
	
A participant is classified as Stable + Response if at no time CFB < -1. Create indicator variable (3 levels) if the relative day of START of Stable or Response falls between D1 and D6, between D7 and D15 and between D16 and D28 for each participant
	
Frequency table and percentage responders in each of the categories defined by the indicator variable, by treatment. Exact 95% confidence intervals for each percentage

Objective 2 6-point ordinal Scale at D6 and D15 and D28 in relation to D-Dimers and complement C5a levels at baseline
		
Box-whisker plot of baseline D-Dimers and complement C5a for each score (x-axis) reported on each of D6, D15 and D28

Objective 2 Change from baseline in SOFA score (https://www.mdcalc.com/sequential-organ-failure-assessment-sofa-score)
	
Change from baseline to D6 and D15 in SOFA score
	
Summary statistics for raw data and change from baseline

Endpoint	Derivation	Analysis
to Day 6, Day 15 (or at discharge, whichever comes first)		

Objective 2
 
Number of days with fever (defined as 37.1°C or more) during 28-day assessment period
	
Create indicator variable for each participant on each day where temperature is above 37.1 °C
 
Create variable with total number of days where temperature was above 37.1 °C for each participant
 
Create variable for each participant giving total number of days where temperature was recorded
	
Summary statistics to provide n, average number of days, SD, median, minimum and maximum where temperature was above 37.1 °C by treatment
 
Produce line plot of temperature over time for each patient together with average line per treatment group.
 
Temperatures are due to be taken daily until discharge – indicate the number of subjects on each day in each treatment arm


Objective 2
 
Time since randomization until absence of LAST fever (defined as 37.1°C or more) for more than 48 h without antipyretics (use last fever to account for possibility that participants have intermittent fever per this definition)
	
Antipyretic use in last 24 hours is collected on eCRF on every day. Use highest temperature recorded in last 24 hours, not the 7-10am temperature to identify the date when the last fever ended per definition.
 
Create variable which contains number of days between this date and date of randomisation for each participant. If a participant has had no episodes of the fever, the number of days is 0.
 
Create indicator variable (censor) to indicate if participant has recovered from the last fever at time of analysis (0=recovered, 1=fever is ongoing at time of analysis). If a participant has had no fever, (i.e. time=0), censor=0.
	
Kaplan-Meier analysis using PROC LIFETEST. Strata ACTARM.
 
Request Failure plot adjusting axis and heading titles to reflect responder and not failure
 
Output statistics:
 
Appropriate statistics from analysis as indicated in mock shell

Endpoint	Derivation	Analysis

Objective 2
 
Duration of hospital stay
 
Duration of hospital stay of survivors
	
Calculate duration of hospital stay in days (Hospital Discharge date-Hospital Admission date)
 
Create indicator variable to flag survivors
	
Summary statistics: n, nmissing, mean, SD, median, minimum, maximum
 
By treatment arm

Objective 2
 
Number of days requiring supplemental oxygenation after randomisation to Day 28 (or discharge, whichever comes earlier)
	
Number of days where Suppl O₂ = ‘Y’ from Vital parameters
	
Summary statistics: n, nmissing, mean, SD, median, minimum, maximum
 
By treatment arm

Objective 2
 
Time since randomization until improvement in oxygenation (defined as independence from supplemental oxygen) during 28 day assessment period (or discharge, whichever comes earlier)
	
Independence from supplementary oxygen means no further ‘Y’ after a ‘N’
	
Kaplan-Meier analysis using PROC LIFETEST. Strata ACTARM.
 
Request Failure plot adjusting axis and heading titles to reflect responder and not failure
 
Output statistics:
 
Appropriate statistics from analysis as indicated in mock shell


Objective 2
 
Number of days with hypoxia (defined as SpO₂ <93% breathing room air or the dependence on supplemental oxygen after randomisation to Day 28 (or discharge, whichever comes earlier)
	
Use SpO₂ (%) and Suppl O₂ (Y/N) from Vital parameters to derive indicator variable which flags each day where this condition holds.
 
Derive variable per participant that gives total number of days with condition
	
Summary statistics of variable with Total number of days: n, mean, SD, median, minimum, maximum
 
By treatment arm

Endpoint	Derivation	Analysis

Objective 3 Duration of ventilator free days after randomisation to Day 28 (or discharge, whichever comes earlier)
	
Use data from Vital parameters (include all days, where NIV, IV and ECMO='N')
	
Summary statistics of variable with Total number of days: n, mean, SD, median, minimum, maximum By treatment arm

Objective 3 Duration of invasive mechanical (including ECMO) and non-invasive mechanical ventilation in ventilated participants
	
Complement of above (exclude participants who are not ventilated i.e. do not include these with a duration of 0)
	
Summary statistics of variable with Total number of days: n, mean, SD, median, minimum, maximum By treatment arm

Objective 3 Time since randomization until first use of high-flow oxygen devices or non-invasive mechanical ventilation or invasive mechanical ventilation or ECMO in non-ventilated participants (i.e. excluding participants who are ventilated within 24h prior to or after randomization) during 28-day assessment period
	
Use Vital Parameter CRF and the method of supplementary oxygen variable. Use the date from this CRF to identify when first use occurred. Indicator variable to identify sub-group to be included. Censor if never used any of these ventilation methods at Day 28
	
Kaplan-Meier analysis using PROC LIFETEST. Strata ACTARM. Request Survival plot adjusting axis and heading titles to reflect progression and not response Output statistics: Appropriate statistics from analysis as indicated in mock shell


Objective 3 Time since randomization to progression to ARDS
	
Randomisation date Date of ARDS diagnosis Derive time variable (days) from date of randomization to date of ARDs diagnosis for each participant. For participants who
	
Kaplan-Meier analysis using PROC LIFETEST. Strata ACTARM. Request Survival plot adjusting axis and heading titles to reflect progression and not response

Endpoint	Derivation	Analysis
	
do not progress to ARDs, time is from date of randomization to date of discharge from hospital or 28 days, whichever is earlier.
 
Derive Censor variable indicating whether Progression to ARDS (censor=0, otherwise censor=1)
	
Output statistics:
 
Appropriate statistics from analysis as indicated in mock shell

Objective 3
 
Duration of ICU stay in participants that enrolled in trial that were on invasive or non-invasive mechanical ventilation or high-flow oxygen devices within 24h prior to or after randomization during 28-day assessment period
 
Duration of ICU stay in participants that enrolled in trial that were on invasive or non-invasive mechanical ventilation for less than 24h prior to or after randomization during 28-day assessment period
	
Use DATES and Vital Signs dataset to calculate variable giving total number of days in ICU for sub-group of patients
	
Summary statistics of variable with Total number of days: n, mean, SD, median, minimum, maximum
 
By treatment arm

Endpoint	Derivation	Analysis

Objective 6 All-cause mortality rate at 28 days post randomisation (all treated participants)
 
All-cause mortality rate at 28 days post randomisation (excluding participants that required invasive mechanical ventilation or ECMO, non-invasive mechanical ventilation or high-flow oxygen devices within 24 hours prior to or after randomisation)
 
All-cause mortality rate at 28 days post randomisation (excluding participants that required invasive mechanical ventilation or ECMO within 24 hours prior to or after randomisation)
 
All-cause mortality rate at 28 days post randomisation (excluding participants that required invasive mechanical ventilation or ECMO, non-invasive mechanical ventilation or high-flow oxygen devices within 24 hours prior to or after randomisation)
 
All-cause mortality rate at 28 days post randomisation (only including participants that required invasive
	
Using 6 point ordinal scores, DATES and VITAL SIGNS and SuppO2 variables :
 
Derive indicator variable identifying each sub-group of patients identified in the Endpoint column
 
Derive Mortality variable identifying whether a patient has died within 28 days of randomisation
	
For each mortality sub-group: PROC LOGISTIC Model: Mortality=ACTARM Output percentage died on each treatment and 95% confidence interval. Odds ratio and 95% confidence interval

Endpoint	Derivation	Analysis

mechanical ventilation or ECMO within 24 hours prior to or after randomisation)
 
All-cause mortality at follow up 12-22 weeks post-randomisation for all treated participants
		

Objective 5
 
Incidents of participants in each category of the 6-point ordinal scale at follow-up 12-22 weeks post randomisation
	
6-point ordinal score
	
PROC FREQ to create summary table of actual counts and percentages for each of the 6-points on the ordinal scale at follow-up by treatment arm


Objective 5
 
Incidents of lung fibrosis on chest high-resolution computed tomography (HRCT) scan at follow up 12-22 weeks post-randomisation
 
Incidents of lung function abnormalities at follow up 12-22 weeks post-randomisation
	
HRCT results
 
Lung function results – dataset should list all abnormalities in a consistent way across participants, including ‘None’
	
Summarise Left lower, Left middle and Left Upper Total Scores by treatment
 
Summarise Right lower, Right middle and Right Upper Total Scores by treatment
 
Provide 100% stacked bars for each of the above 6 areas, coding by score (normal, reticular, bronch and honeycomb) – a separate graph for each treatment

Objective 5
 
Results from the 6-minute walk test
		

Endpoint	Derivation	Analysis

Objective 5
 
Incidents of participants in each category of the WHO performance scale
	
WHO score
	
Summary statistics of WHO Score by treatment at follow-up

Objective 4
 
Incidence of nosocomial bacterial or invasive fungal infection during 28-day assessment period
 
Note: Participants with viral respiratory infection are at risk of secondary bacterial infections. As part of clinical routine care, sputum or BAL samples will be collected in participants suspected of secondary bacterial pneumonia and checked for presence of bacteria. Measurements of procalcitonin levels will be performed at least 3x/week until 14 days or hospital discharge
	
Procalcitonine will be concentrations. Concentrations are to be taken 3 times a week. The actual day each week may differ between participants. Allocate 1, 2 or 3 to each concentration taken in chronological order in each week.
 
Replace ‘Not Detectable’ with the lower limit of quantification and include in the summary statistics.
 
Data for bacteria will be presence/absence at each day tested (if collected)
	
Summarise procalcitonine concentrations by occasion (1,2,3) within each period of 7 relative days post first-dose for each treatment.
 
Summary statistics to include n, nmissing, Mean, SD, Median, Minimum, Maximum. n in each case will be N-Not Done(nmissing).
 
Provide line plots over relative day by treatment. A separate line for each participant
 
Depending on distribution of data the above summary statistics will be provided using the log scale, and presented after back transforming


No specific objective
 
Change in ferritin levels between D1 and D6 and between D1 and D15 (or discharge in each case)
 
Change in CRP levels between D1 and D6 and between D1 and D15 (or discharge in each case)
	
Laboratory values – derive change from D1 (i.e the last pre-dose value) to D6 and D15 or day of discharge
	
Summarise change from D1 in concentrations to D6 and to D15 (or day of discharge) for each treatment.
 
Summary statistics to include n, nmissing, Mean, SD, Median, Minimum, Maximum. n in each case will be N-Not Done(nmissing).

Endpoint	Derivation	Analysis
		Provide line plots over relative by treatment, for both absolute values and change from D1. A separate line for each participant

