2.3 Study design and conduct

This investigator-initiated trial is a phase 2 academic, prospective, 2:1 randomized, open-label, multi-center interventional study designed to investigate the efficacy of subcutaneous Zilucoplan® in improving oxygenation and short- and long-term outcome of COVID-19 participants with acute hypoxic respiratory failure.

Several academic and non-academic centers in Belgium will participate in this trial. Study coordination, monitoring and data management will be performed under the responsibility of the Health Innovation and Research Institute UZ Gent (HIRUZ) Clinical Trial Unit and Data Management Unit.

[figure not shown]
81 participants with confirmed COVID19 with acute hypoxic respiratory failure (saturation below 93% on minimal 2 L/min supplemental O₂ or PaO₂/FiO₂ <350) will be randomised to receive up to 14 days of SC Zilucoplan® on top of standard of care (active Arm A), or to receive standard of care treatment (control Arm B). Randomization will be done at a 2:1 ratio active: control group. In the active Arm A and in the control Arm B, participants will additionally receive daily antibiotics (daily 3rd generation cephalosporin IV while in hospital, followed by oral ciprofloxacin while discharged) as primary prophylaxis against meningococcal disease until 14 days after the last dose of Zilucoplan®. Control Arm B will receive standard of care and prophylactic antibiotics (3rd generation cephalosporin IV) for only 1 week (or until hospital discharge whichever comes first), to control for the effects of antibiotics on the clinical course of COVID-19.

A schematic of the study design is provided in Figure 1.

To measure the effectiveness of Zilucoplan® on restoring lung homeostasis, the primary endpoints of this intervention is measuring change in oxygenation comparing change from baseline values (pre-treatment) to values pre-dose day 6 (or discharge whichever comes first) and to values at day 15 (or discharge whichever comes first) post-randomization between Arm A and Arm B.

The study is estimated to terminate 52 weeks after the first participant is dosed, including last clinical follow up visits.

Figure 1 Description of Study Design

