2.4 Determination of sample size

The outcome(s) on which the sample size calculation is based upon, is the primary endpoint measurement of oxygenation, defined as ratio of PaO₂/FiO₂.

The target difference is the difference from baseline measured at the primary endpoint (at day 6 and day 15) between the control and the treated group. Given a sample size of 81 participants, 54 on Zilucoplan® and standard of care and 27 on standard of care there would be >85% power to show a significant difference from standard of care at the 2 sided 5% level if the true underlying treatment difference was an 80 point difference (25% of 320, being the mean at hospital admission) in the PaO₂/FiO₂ ratio. This assumes a standard deviation of 105 and a dropout rate of less than 10%.

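### The final logistic model for the 6-point scale enters the score as a fixed effect (Score*Treatment), so it yields no single treatment effect with a confidence interval, and the SAP leaves the status of code 7 in that model open

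*SAP*

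**What the plan says.** The row of SAP Table 8.1 on the distribution of the 6-point scale at D1, D6, D15 and D28 gives the final analysis as "Logistic regression for data from specified nominal days (D1, D6, D15 and D28"), with a "Fixed effect of Score*Treatment indicating whether the pattern across scores is different between treatments on each day". Nothing further is specified: no response variable, no choice between binary, cumulative and generalized logit, no treatment main effect, no baseline score, and no allowance for repeated measurements on a participant.

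The derivation column of the same row adds a code: "An additional category (score=7) to be created to indicate participants who have withdrawn from the study for any reason or transferred to another hospital". Code 7 is carried forward to later days. It counts in the percentages and appears in the stacked bar chart, "color coded for scores 1-7 (including 8 in the interim analyses"), while the frequency table is described as covering the six points only. The next row, change from baseline, bars the added codes. The logistic row neither bars nor includes them.

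Three other statements bear on this:

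- SAP 3.1: models for secondary endpoints are fitted for estimation, with 95% confidence limits and no p-values.
- The text before Table 8.1: for variables that use data only up to discharge or transfer, participants who withdraw or are transferred are set to missing for later periods.
- A note in the logistic row: D1 is left out of the table and plot if it is pre-dose. The note does not mention the model.

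**The concern.** A regression needs an outcome on one side and predictors on the other. Here the outcome appears inside the predictor and the other side is blank. Two programmers could fit different models from this sentence, and none of the natural readings gives one directional treatment effect with an interval.

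The row is out of line with its neighbours. The sustained 2-point improvement row states its response, its arm term, an odds ratio and a 95% interval. The change-from-baseline row names its response and every model term.

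Code 7 adds a second ambiguity. A higher score is better on this scale and 6 is not hospitalized. If a programmer passed codes 1-7 to an ordinal procedure, a withdrawn or transferred participant would rank above a discharged one.

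**Working it through.** **Inputs from the SAP.** Allocation: "Randomization will be done at a 2:1 ratio active: control group", 54 v 27. The only power statement is for the primary PaO2/FiO2 ratio: "there would be >85% power to show a significant difference from standard of care at the 2 sided 5% level". It rests on an effect of 80 points on that ratio, an SD of 105 and fewer than 10% lost. No power or precision is given for the ordinal scale.

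**The plan's own figure.** SE = 105 × √(1/27 + 1/54) = 24.75; 80/24.75 = 3.232; power = Φ(3.232 − 1.960) = 89.8%. With 10% lost (24.3 v 48.6): SE = 26.09; 80/26.09 = 3.067; power = Φ(1.107) = 86.6%. The stated figure reproduces. It says nothing about the model discussed here.

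**Assumptions, not in the documents.** Shares for scores 1 to 6 at D28 of 12, 5, 3, 5, 5 and 70%, and withdrawal unrelated to outcome.

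**Reading 1: homogeneity test.** As a log-linear Score*Treatment term, or as arm regressed on nominal score, the model gives the likelihood-ratio test of the arm-by-score table (9.609 by all three routes on one simulated data set). In 3000 simulated null trials with 5% coded 7 in each arm, type I error was 5.1% at 5400 v 2700 and 8.4% at 54 v 27, where categories are sparse. The test has no direction, and SAP 3.1 would not report its p-value.

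**Reading 2: category-specific odds ratios.** The coefficients of the log-linear model are log odds ratios for each category against a reference. Expected counts for scores 1 to 6:

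- Arm A: 6.48, 2.70, 1.62, 2.70, 2.70, 37.8
- Arm B: 3.24, 1.35, 0.81, 1.35, 1.35, 18.9

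With score 6 as reference and no treatment effect, SE = √(sum of the four reciprocal counts), and the limits are the estimate divided and multiplied by exp(1.96 × SE).

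| Comparison | SE of log OR | Factor either side |
|---|---|---|
| Score 1 v 6 | √0.542 = 0.736 | 4.2 |
| Score 2, 4 or 5 v 6 | √1.190 = 1.091 | 8.5 |
| Score 3 v 6 | √1.931 = 1.390 | 15.2 |

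For one common odds ratio from a cumulative-logit model, information = [54 × 27/(3 × 81)] × (1 − Σp³) = 6 × (1 − 0.3451) = 3.929. SE = 1/√3.929 = 0.504 and the factor is exp(1.96 × 0.504) = 2.7, before any gain from baseline score.

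**Reading 3: events/trials.** With score, treatment and their interaction, each participant is counted once per category. The counts within an arm sum to the arm size, so they are negatively correlated, but the model treats them as independent and understates the variance of contrasts between categories. Simulated type I error was 14.3% at 54 v 27 and 9.4% even at 5400 v 2700, so sparseness is not the only cause.

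**Code 7, if ranked as the top level.** If 10% of Arm A and none of Arm B is coded 7, and the arms are otherwise identical, the probability that an Arm A participant ranks better is 0.10 × 1 + 0.90 × 0.5 = 0.55 instead of 0.50. Fitted common odds ratios:

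| Withdrawn, A v B | True OR 1.0 | True OR 2.0 |
|---|---|---|
| 10% v 0% | 1.50 | 2.80 |
| 0% v 10% | 0.63 | 1.08 |
| 5% v 5% | 1.00 | 1.78 |
| 10% v 10% | 1.00 | 1.61 |

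With code 7 left out, the same fits return 1.00 and 2.00 throughout. Code 7 as a nominal level does not rank withdrawal above discharge.

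**The case against.** The strongest reply is that the sentence can be read sensibly. A Score*Treatment term in a log-linear or generalized-logit model is a recognised way to compare distributions; it gives valid category-specific odds ratios with intervals, and SAP 3.1 promises limits for comparisons of interest, not one summary ratio per endpoint. That stands: the model is not meaningless. It remains a set of imprecise contrasts without direction or baseline adjustment, and the SAP does not say that this reading is meant.

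A reader might infer that the SAP ranks withdrawal above discharge and so rewards drop-out. The documents do not support this. Code 7 is introduced as a labelled category for percentages and the bar chart, and the frequency table covers six points. The companion code 8 marks interim participants still on treatment, which can hardly mean better than discharge. The bias above is conditional on a use the SAP never states.

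A reader might also infer that the plan yields no valid treatment effect on this scale. It does, in other rows of Table 8.1 that do not use code 7: a baseline-adjusted MMRM, a Kaplan-Meier analysis of time to improvement, an odds ratio for sustained improvement, and a baseline-adjusted analysis of AUEC/Time. Nor is this row shown to be the main clinical secondary endpoint: Protocol 4.2 lists category incidence only at the 12-22 week follow-up.

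The note on pre-dose D1 shows the intent, though it stops short of the model. The mock shells may hold more detail, but the response variable belongs in the SAP.

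**Conclusion.** The model as written is not specified well enough to give a treatment effect, and the role of code 7 in it is undefined. The evident readings give an undirected test whose p-value would not be reported, odds ratios with limits a factor of 4.2 to 15.2 either side, or an events/trials fit with type I error of 14.3%. A single common odds ratio would have limits a factor of 2.7 either side.

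These sizes rest on the assumed category shares and are illustrative. A simulated comparison at an odds ratio of 2.5, also with assumed shares, points the same way: about 25-38% power for the pattern test and 38-57% for an ordinal test. Power matters here only as a guide to precision, because secondary endpoints carry no p-values. That the outcome sits in the predictor and no response is named does not depend on any assumption.

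The consequence is limited to one secondary, exploratory analysis. The primary analysis and the other analyses of this scale are unaffected.

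**What to change.** Replace the final-analysis cell with a proportional-odds (cumulative-logit) model: scores 1-6 as the ordered response on D6, D15 and D28, fitted by day or jointly with a participant effect; treatment and baseline score as predictors; the common odds ratio with its 95% interval as the output.

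Add three statements:

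- Codes 7 and 8 are for tables and charts only.
- Participants who withdraw or are transferred are missing in the model after last contact, in line with the text before Table 8.1 and the change-from-baseline row. Deaths and discharges due to improvement keep scores 1 and 6, as now.
- Pre-dose D1 is the baseline covariate, not an outcome day.

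The cost is one table cell and no new data. The price is reliance on proportional odds, which readers can check against the planned category tables, and on missingness being unrelated to outcome given treatment and baseline score for those who leave.
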